5.3 STRATEGIES FOR RECRUITMENT AND RETENTION

Recruitment of the 25 participants for this trial will occur from new or established patients treated at the Hematology Clinic at Moffitt Cancer Center. Screen failure is anticipated to be less than 10%. The target accrual is expected to be reached in 18-24 months. All faculty members in the Lymphoma Section will be sub-investigators on the trial. They will be trained on the trial design, study agents, and eligibility criteria. This will equip each investigator to discuss the trial with potential participants as appropriate. The trial will be listed on the Moffitt Cancer Center website (www.moffitt.org) for the availability of local physicians to refer patients who could be eligible for the trial.

All investigators will be made aware of the emphasis to enroll women and minorities. The design of the trial and eligibility criteria are not restrictive relative to women and minorities. As stated in the background section of the protocol, CLL affects more males than females (1.7:1) [2-4]. The clinical research team for this trial has experience with recruiting in another frontline investigator-initiated trial (MCC16622). Of the 45 participants accrued, 15 were women. The sex, ethnicity, and race of each participant on this trial will be captured in the Oncore electronic data base for reporting purposes.

Median age at diagnosis of CLL patients is between 67 and 72 years [2]. Therefore, strategies for retention of elderly participants must be considered. Older adults may have medical conditions that cause them to drop out if side effects are severe or interact with medical treatment for comorbidities [58]. They are often concerned with cost of travel or distance to the study site. Moffitt Cancer Center has the unique barrier to enrollment of patients who may decline participation or want to discontinue as they live in Florida only during the winter months. Researchers have examined patient satisfaction in older adults and determined having continuity in staff and frequent visits increases the sense of being treated in a thorough manner [58]. This relationship building promotes retention. Potential participants will be assessed prior to screening for any perceived barriers related to the clinical trial process. Referrals will be made to a social worker, supportive care services, financial services, or the research nurse to address barriers prior to consent. Once consented, the participant will have contact with the research nurse at a minimum of every three to four weeks during treatment for the duration of the 12 month treatment process.

5.4 PARTICIPANT WITHDRAWAL OR TERMINATION

5.4.1 REASONS FOR WITHDRAWAL OR TERMINATION

Subjects may withdraw consent at any time for any reason or be dropped from the trial at the discretion of the investigator should any untoward effect occur that may jeopardize participant safety. In addition, a subject may be withdrawn by the investigator if enrollment into the trial is inappropriate, the trial plan is violated, or for administrative and/or other safety reasons.

A subject must be discontinued from the trial for any of the following reasons:

- The subject or legal representative (such as a parent or legal guardian) withdraws consent.
- Unacceptable adverse events
- Intercurrent illness that prevents further administration of treatment
- Investigator's decision to withdraw the subject
- The subject has a confirmed positive serum pregnancy test
- Noncompliance with trial treatment or procedure requirements
- The subject is lost to follow-up
- Administrative reasons

The End of Treatment and Follow-up visit procedures are listed in Section 7.3.7 (schedule of events) and Section 7.3 (Visit Requirements). After the end of treatment, each subject will be followed until 90 days after the end of pembrolizumab infusions and 30 days after the last dose of ibrutinib. (serious adverse events will be collected for 90 days after the end of treatment as described in Section 7.2.3.1). The last dispensing of ibrutinib will occur at week 51 and dosing will continue for an additional 3 weeks. Subjects who discontinue for reasons other than progressive disease will have post-treatment follow-up for disease status and toxicity up to 30 days after stopping ibrutinib and 90 days after stopping pembrolizumab. Follow-up rules will apply unless participant initiates a non-study cancer treatment, withdraws consent, or becomes lost to follow-up (unsuccessful attempts to contact for 3 months). After documented disease progression each subject will be followed by telephone every 12 weeks for overall survival until death, withdrawal of consent, or the end of the study, whichever occurs first.

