7.3.3 FOLLOW-UP

Follow-Up Visits (every 12 weeks +/- 7 days after Safety Visit up to 12 months)

- Directed physical examination, vital signs and brief review of systems.
- Survival status and anti-cancer therapy status
- Medication reconciliation.
- Toxicity/ AE assessment
- ECOG performance status assessment.
- Hematology (hemoglobin, HCT, RBC, WBC with differential [neutrophils, bands, lymphocytes, monocytes, eosinophils and basophils])
- Chemistry (ALT, AST, alkaline phosphatase, total bilirubin, LDH, calcium, bicarbonate, sodium, potassium, chloride, creatinine, BUN, total protein and albumin)

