¹⁰ Tumor imaging will consist of CT of the neck, chest, abdomen and pelvis that will be performed at screening, if not done within 3 months prior to study entry. Response assessment will be done at week 12, week 24, and end of 51 weeks of treatment. CT scans may be performed at different intervals at investigator discretion (i.e. suspicion of progressive disease). Imaging studies post treatment discontinuation will be performed per investigator discretion (including end of treatment imaging assessment).

¹¹ Bone marrow biopsy will be performed at screening (if not performed within 30 days) and after the end of pembrolizumab and ibrutinib therapy (28-35 days after week 51). If subject discontinues treatment early or progression of disease is suspected, a bone marrow biopsy will be per investigator discretion. During follow-up, bone marrow biopsies will be performed per investigator discretion.

¹² Correlative studies. Please refer to Section 4.1 for biomarkers to be studied. They will be performed at baseline (prior to first dose of study drug), at week 6, week 21, and end of ibrutinib treatment. See Section 7.2 for correlative sample collection procedure. They will be performed at investigator's discretion if early study termination

¹³ Safety follow-up will be 90 days after the end of pembrolizumab treatment (may be at the regularly scheduled monthly visit that is nearest to 90 days if continuing on ibrutinib treatment) and 30 days post discontinuation of ibrutinib treatment. If the subject discontinues early, safety follow up must occur before first dose of the next therapy.

¹⁴ Follow-up after a subject has discontinued trial treatment will be every 12 weeks for 12 months.

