10.2.2 ANALYSIS OF THE SECONDARY ENDPOINT(S)

1. Change in T cell exhaustion and/or inhibition following treatment
2. Change in serum immunoglobulin levels following treatment
3. Progression free survival (PFS) and association with immune biomarkers

To determine if T cell exhaustion or inhibition have change due to treatment with the combination therapy at baseline immune testing to immune testing following completion of pembrolizumab and ibrutinib treatments (week 52) using paired t-tests with the null hypothesis being that there is no change in immune measurements following treatment (i.e., $H_0: \mu_d = 0$). If the assumptions of normality do not hold upon assessment, we will instead use nonparametric t-tests (i.e., Wilcoxon Sign Rank Test). Similar tests will be used to determine if changes in serum immunoglobulin levels also resulted following treatment. Tests will be one-sided as based on biology expect the change in immune response to be in one direction following treatment. Tests will be considered statistically significant if the p-value is less than 0.05. Assuming the study go on to stage II and enroll 25 patients, we will be able to detect a modest effect size of 0.60. To determine the association of progression free survival (PFS) with immune biomarkers (T cell exhaustion and/or inhibition, serum immunoglobulin levels), Cox proportional hazards models will be fit with assumption of proportional hazards (PH) assumption check via Schoenfeld residuals. If the PH assumption does not hold, we will rely on use of non-parametric methods (Kaplan-Meier curve with log-rank tests) where the biomarkers will be dichotomized for analysis based on an optimal cut-point determination based on an outcome-oriented approach outlined by Contral and O'Quigley (Contal C, O'Quigley J. An application of changepoint methods in studying the effect of age on survival in breast cancer. Computational Statistics & Data Analysis. 1999;30:253-70.). A Cox regression of the log hazard ratio on the continuous biomarker (assuming a standard deviation of 1 and an anticipated event rate of 0.50) will have 80% power at a 0.05 significance level to detect a regression coefficient equal to 0.79 (i.e., hazard ratio of 2.20).

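### Section 5.4.1 ends disease-status follow-up 30/90 days after treatment while 7.3.3 and the schedule run visits for 12 months; PFS events are lost under the shorter rule, and the 0.50 event rate has no stated basis under either

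*Combined protocol and SAP*

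**What the plan says.** Section 5.4.1 first states that every subject is followed to 90 days after the last pembrolizumab infusion and 30 days after the last ibrutinib dose. It then says that those who stop for a reason other than progression "will have post-treatment follow-up for disease status and toxicity up to 30 days after stopping ibrutinib and 90 days after stopping pembrolizumab". Subjects with documented progression move to 12-weekly telephone contact for survival.

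Section 7.3.3 is headed "Follow-Up Visits (every 12 weeks +/- 7 days after Safety Visit up to 12 months", and footnote 14 of the schedule in 7.3.7 says "Follow-up after a subject has discontinued trial treatment will be every 12 weeks for 12 months". The Study Summary gives a participant duration of two years, which fits about one year of treatment plus one year of follow-up.

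Section 4.2.2 lists PFS and Richter's transformation as secondary endpoints. Section 10.2.2 plans a Cox model of PFS on immune biomarkers. It is sized "assuming a standard deviation of 1 and an anticipated event rate of 0.50", and the text says that it "will have 80% power at a 0.05 significance level to detect a regression coefficient equal to 0.79 (i.e., hazard ratio of 2.20". The protocol gives no median PFS, no PFS horizon and no censoring rule.

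**The concern.** The two follow-up rules cannot both be applied. The sentence in 5.4.1 names disease status, so it cannot be read as a safety window only, even though 30 and 90 days are also the adverse-event windows in section 8.3.

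If staff follow 5.4.1, subjects without progression leave observation soon after treatment, while those who have already progressed are contacted until death or study end. The people still at risk of a PFS event are then watched least. Early discontinuers are affected most, and if they stopped for toxicity their early censoring may be informative. Richter's transformation, which Appendix C counts as progression, would be missed in the same way. If practice is mixed, the censoring time depends on which section was applied to which patient. Disease status not recorded during follow-up may not be recoverable later.

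**Working it through.** **1. The plan's own Cox figure.** Inputs from 10.2.2: log hazard ratio 0.79 per SD, SD 1, alpha 0.05, power 80%, event rate 0.50. The sample size of 25 comes from the same section ("Assuming the study go on to stage II and enroll 25 patients").

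- Events needed: D = (1.960 + 0.842)² / (1² × 0.79²) = 12.58.
- Patients: 12.58 / 0.50 = 25.15.
- At 25 patients, D = 12.5 and power = Φ(√12.5 × 0.79 − 1.960) = 79.8%; exp(0.79) = 2.20.

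The stated figure reproduces with a two-sided test. A one-sided test would need 9.91 events and give 87.5% at 12.5 events, which does not match. The one-sided statement in that section concerns the paired immune tests.

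**2. Observation time for a completer.** Weeks are counted from first pembrolizumab, with 52/12 weeks per month. The end of ibrutinib reads differently in the protocol: week 54 from 5.4.1 and schedule footnote 2, or about week 60 from 4.1 (54 weeks of ibrutinib starting at week 6). Those passages need reconciling; both readings are carried here.

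- Short rule, week 54 + 30 days: 54 + 30/7 = 58.3 weeks = 13.5 months.
- Short rule, week 51 + 90 days: 51 + 90/7 = 63.9 weeks = 14.7 months.
- Short rule, week 60 + 30 days: 60 + 30/7 = 64.3 weeks = 14.8 months.
- Long rule, week 54 + 30 days + 52 weeks: 110.3 weeks = 25.5 months.
- Long rule, week 60 + 35 days (late edge of the Safety Visit window) + 52 weeks: 117 weeks = 27.0 months.

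Footnote 14 counts the 12 months from discontinuation, not from the Safety Visit, so on its wording the long horizon is about a month earlier (54 + 52 = 106 weeks, 24.5 months).

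For a subject who stops both drugs at week 12, the short rule ends at 12 + 90/7 = week 25 and the long rule at 12 + 30/7 + 52 = week 68.

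**3. Effect on events and power.** The short rule can never give more PFS events than the long one. It gives fewer whenever a progression falls between the two horizons, whatever the event-time distribution. To size the loss a median must be assumed. The table takes exponential PFS from first dose, 25 completers, no loss to follow-up, no pembrolizumab extension, and horizons of 63.9 and 110.3 weeks. Event fraction = 1 − 2^(−t/median); D = 25 × fraction; power = Φ(√D × 0.79 − 1.960).

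Worked case, median 24 months, short rule: 1 − 2^(−14.7/24) = 0.347, D = 8.7, power = 64%.

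| Assumed median PFS (months) | Events, short vs long | Power at HR 2.20, short vs long |
|---|---|---|
| 12 | 14.3 vs 19.3 | 85% vs 93% |
| 15 | 12.3 vs 17.3 | 79% vs 91% |
| 24 | 8.7 vs 13.0 | 64% vs 81% |
| 36 | 6.2 vs 9.7 | 50% vs 69% |
| 60 | 3.9 vs 6.4 | 35% vs 51% |

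**4. What 0.50 implies.** An event fraction of one half is reached when the horizon equals the median. Under the short rule this means a median of about 13.5 to 15 months or less; under the long rule, about 25 to 27 months or less.

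**The case against.** A reader might infer that the short rule cannot support the 0.50 event rate, or that power drops from 80% to about 62%. The documents do not support either as a flat statement. The 62% arises only if 0.50 is assumed to hold at the long horizon: 1 − 0.5^(14.7/25.4) = 0.330, or 8.3 events. With a median of 12 months the short rule alone gives 85% power. Nor does the long rule secure 0.50; at a median of 36 months it gives 69%.

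A reader might also take 7.3.3 as already requiring 12 months of disease assessment. It does not name disease status. It lists survival and anti-cancer therapy status, examination, hematology, chemistry and other items, while sections 7.1.15 and 7.1.16 leave follow-up CT and marrow to the investigator. Examination and counts can show some progression under Appendix C, but the assessment is inferred.

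Other points on that side stand in part:

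- Section 5.4.1 refers to 7.3 and 7.3.7 for follow-up procedures, which with the two-year duration favours the longer schedule. The disease-status sentence still contradicts it.
- Pembrolizumab may be extended to 2 years. For those subjects the short rule reaches 104 + 90/7 = 116.9 weeks, about 27 months. The long rule is also counted from the end of treatment, so the conflict remains.
- The trial has one centre, so inconsistency would arise between patients or staff, not between sites.
- The primary decision rests on complete response under the two-stage design and is untouched.

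**Conclusion.** The contradiction is real and bears on PFS and Richter's transformation. For a completer without extension it moves the censoring time by roughly 11 months (110.3 − 63.9 = 46.4 weeks), and the short rule costs events. Under the assumptions of the table, the loss in Cox power is 12 percentage points at a median of 15 months, 17 at 24 months and 19 at 36 months. These are illustrations over assumed medians, since the protocol supplies none.

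The stated 80% power is arithmetically correct. Its weakness is the 0.50 input, which is tied to no horizon or median. This should be corrected, but it concerns a secondary analysis and does not threaten the primary endpoint.

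**What to change.** In 5.4.1, confine the 30- and 90-day windows to adverse-event collection. State there that subjects without progression have disease status recorded at the 12-weekly visits for 12 months, and add disease status by name to the list in 7.3.3. It can be drawn from the examination and hematology already scheduled, with imaging left at discretion as now. Make the starting point of the 12 months the same in 7.3.3 and footnote 14.

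In 10.2.2, state the PFS horizon, the censoring rule and the median PFS behind the 0.50 event rate.

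If the short window is what the sponsor intends, correct 7.3.3 and footnote 14 to match, check the two-year participant duration, and restate the Cox power for the event rate that the sponsor expects at that horizon.

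The cost is a short text amendment. The recommended version adds no visits or procedures, only a recorded disease-status entry at visits already planned.

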5.4.2 HANDLING OF PARTICIPANT WITHDRAWALS OR TERMINATION

Every effort will be made to maintain contact with a subject who withdraws early. If the subject remains at MCC for further care, clinic visits may be tracked and the condition of the subject followed. If the subject is not continuing care at MCC, contact information will be updated at the end of treatment visit, including accurate phone numbers, and email address. The importance of the follow-up period for AEs and SAEs will be stressed to the subject.

Replacement of participants who screen fail or drop out prior to completing 9 weeks of treatment are permitted to be replaced in order to meet the accrual goal of this study.

5.5 PREMATURE TERMINATION OR SUSPENSION OF STUDY

This study may be temporarily suspended or prematurely terminated if there is sufficient reasonable cause. Written notification, documenting the reason for study suspension or termination, will be provided by the suspending or terminating party to investigator, funding agency, the IND/IDE sponsor and regulatory authorities. If the study is prematurely terminated or suspended, the PI will promptly inform the IRB and will provide the reason(s) for the termination or suspension.

Circumstances that may warrant termination or suspension include, but are not limited to:

1. Quality or quantity of data recording is inaccurate or incomplete
2. Poor adherence to protocol and regulatory requirements
3. Incidence or severity of adverse drug reaction in this or other studies indicates a potential health hazard to subjects
4. Plans to modify or discontinue the development of the study drug
5. Determination of futility

In the event Merck or Janssen decide to no longer supply study drug, ample notification will be provided so that appropriate adjustments to subject treatment can be made.

6 STUDY AGENT

6.1 STUDY AGENT(S) AND CONTROL DESCRIPTION

6.1.1 ACQUISITION

Investigational products for this trial will be supplied by Merck & Co, Inc. (pembrolizumab) and Janssen Pharmaceuticals, Inc. (ibrutinib).

Pembrolizumab

An order form supplied by Merck will be utilized. The form will have instructions on how to order. Pharmacy will complete the quantity needed and the shipment address. Orders will require 7 business days to arrive on site.

Ibrutinib

Ibrutinib will be shipped from Janssen as bottles of capsules. For the initial supply, the Janssen trial manager will make arrangements for shipment of bottles expected to be used in the first one to two months, dependent on planned enrollment. Future re-orders will be submitted using a drug request form supplied by Janssen. Order forms will be submitted by email to the team email address ([contact]) printed on the order form. Allow 7 business days for drug to arrive on site.

6.1.2 FORMULATION, APPEARANCE, PACKAGING, AND LABELING

IBRUTINIB

Ibrutinib is an inhibitor of Bruton's tyrosine kinase (BTK). Ibrutinib is a small-molecule inhibitor of BTK. Ibrutinib forms a covalent bond with a cysteine residue in the BTK active site, leading to inhibition of BTK enzymatic activity. BTK is a signaling molecule of the B-cell antigen receptor (BCR) and cytokine receptor pathways. BTK's role in signaling through the B-cell surface receptors results in activation of pathways necessary for B-cell trafficking, chemotaxis, and adhesion. Nonclinical studies show that ibrutinib inhibits malignant B-cell proliferation and survival in vivo as well as cell migration and substrate adhesion in vitro. It is a white to off-white solid with the empirical formula C25H24N6O2 and a molecular weight 440.50. Ibrutinib is freely soluble in dimethyl sulfoxide, soluble in methanol and practically insoluble in water. Ibrutinib capsules for oral administration are supplied as white opaque capsules that contain 140 mg ibrutinib as the active ingredient. Each capsule also contains the following inactive ingredients: croscarmellose sodium, magnesium stearate, microcrystalline cellulose, sodium lauryl sulfate. The capsule shell contains gelatin, titanium dioxide and black ink. Each white opaque capsule is marked with "ibr 140 mg" in black ink. Clinical supplies will be affixed with a clinical label in accordance with regulatory requirements.

The white opaque 140 mg capsules marked with "ibr 140 mg" in black ink are available in white HDPE bottles with a child-resistant closure:

- 90 capsules per bottle: NDC 57962-140-09

PEMBROLIZUMAB

Pembrolizumab is a humanized monoclonal antibody that blocks the interaction between PD-1 and its ligands, PD-L1 and PD-L2. Pembrolizumab is an IgG4 kappa immunoglobulin with an approximate molecular weight of 149 kDa. Binding of the PD-1 ligands, PD-L1 and PD-L2, to the PD-1 receptor found on T cells, inhibits T cell proliferation and cytokine production. Upregulation of PD-1 ligands occur in some tumors and signaling through this pathway can contribute to inhibition of active T-cell immune surveillance of tumors. Pembrolizumab is a monoclonal antibody that binds to the PD-1 receptor and blocks its interaction with PD-L1 and PD-L2, releasing PD-1 pathway-mediated inhibition of the immune response, including the anti-tumor immune response. In syngeneic mouse tumor models, blocking PD-1 activity resulted in decreased tumor growth.

Based on dose/exposure efficacy and safety relationships, there are no clinically significant differences in efficacy and safety between pembrolizumab doses of 200 mg or 2 mg/kg every 3 weeks in patients with

NSCLC

Pembrolizumab injection will be provided as a sterile, preservative-free, clear to slightly opalescent, colorless to slightly yellow solution that requires dilution for intravenous infusion. Each vial contains 100 mg of pembrolizumab in 4 mL of solution. Each 1 mL of solution contains 25 mg of pembrolizumab and is formulated in: L-histidine (1.55 mg), polysorbate 80 (0.2 mg), sucrose (70 mg), and Water for Injection, USP.

6.1.3 PRODUCT STORAGE AND STABILITY

IBRUTINIB

Store bottles at room temperature 20°C to 25°C (68°F to 77°F). Excursions are permitted between 15°C and 30°C (59°F to 86°F). Retain in original package until dispensing.

PEMBROLIZUMAB

Pembrolizumab for injection (lyophilized powder): carton containing one 50 mg single-dose vial (NDC 0006- 3029-02). Store vials under refrigeration at 2°C to 8°C (36°F to 46°F).

Pembrolizumab injection (solution): carton containing one 100 mg/4 mL (25 mg/mL), single-dose vial (NDC 0006-3026-02). Store vials under refrigeration at 2°C to 8°C (36°F to 46°F) in original carton to protect from light. Do not freeze. Do not shake.

